Clinical Trial Protocol

Document Number:	c03317678-02							
2015-000404-25								
1358.1	1358.1							
Diclofenac + Capsaicin								
A randomized, controlled multi-ce assess the efficacy and safety of m applied combination containing did 0.075% (2 g formulation per applied 5 days) compared to placebo, as w capsaicin 0.075% in patients with a	ultiple doses of a topically clofenac 2% + capsaicin cation; 2-times daily for ell as to diclofenac 2% and							
Capsaicin/diclofenac gel in acute b	pack pain or neck pain							
III								
Phone: , Fa	x:							
Phone: , Fax	:							
Final Protocol								
Version: 2.0	Date: 21 Jun 2016							
Page 1 of 69								
	2015-000404-25 1358.1 Diclofenac + Capsaicin A randomized, controlled multi-ce assess the efficacy and safety of mapplied combination containing dio 0.075% (2 g formulation per applied 5 days) compared to placebo, as we capsaicin 0.075% in patients with a Capsaicin/diclofenac gel in acute but III Phone:							

Proprietary confidential information.

© 2016 Boehringer Ingelheim International GmbH or one or more of its affiliated companies. All rights reserved. This document may not - in full or in part - be passed on, reproduced, published or otherwise used without prior written permission.

c03317678-02 Trial Protocol Page 2 of 69

Proprietary confidential information © 2016 Boehringer Ingelheim International GmbH or one or more of its affiliated companies

CLINICAL TRIAL PROTOCOL SYNOPSIS

Name of company:		Boehringer Ingelheim					
Name of finished produ	ct:						
Name of active ingredie	ent:	Diclofenac + Capsaicin					
Protocol date:	Trial number:		Revision date:				
09-Dec-2015	1358.1		21-Jun-2016				
Title of trial:	A randomized, controlled multi-centre parallel group study to assess the efficacy and safety of multiple doses of a topically applied combination containing diclofenac 2% + capsaicin 0.075% (2 g formulation per applicati 2-times daily for 5 days) compared to placebo, as well as to diclofenac 2% a capsaicin 0.075% in patients with acute back or neck pain						
Coordinating Investigator:							
Trial site(s):	Phone:	, Fax: nducted in 2 countries					
Clinical phase:	III	nducted in 2 countries					
Objective(s):	To assess the efficacy combination of diclo	y and tolerability of a topical form fenac and capsaicin in comparison e, and placebo for the treatment of	to gels with diclofenac				
	formulation containing over placebo and over 0.075% capsaicin alcoholomatical A secondary objective.	re of this trial is to demonstrate sup ng a combination of 2% diclofenate or formulations containing 2% diclorence for the treatment of acute back are is to assess the safety and toleral osaicin in comparison to gels with	c and 0.075% capsaicin ofenac alone and or neck pain.				
Methodology:		-blind, placebo- and active-control	lled, multi-centre 4-arm				
No of notionts	parallel group study,	conducted in 2 countries					
No. of patients: total entered:	Approximately 800 t	o achieve 700 patients eligible for	the assessment of the				
each treatment:	Diclofenac and capsa Diclofenac: Capsaicin: Placebo:	240 240 80					
Diagnosis:	Acute back pain or n	eck pain					

c03317678-02 Trial Protocol Page 3 of 69

Proprietary confidential information © 2016 Boehringer Ingelheim International GmbH or one or more of its affiliated companies

	Diclofenac + Capsaicin							
l number:		Revision date:						
3.1		21-Jun-2016						
Male or female patients ≥ 18 years with current diagnosis of acute back pain of neck pain. Acute back pain or acute neck pain resulting in pain on movement (POM) ≥50 mm (VAS 0-100) for at least one POM procedure out of 5 standardized procedures.								
	etric pressure on the painful trigger	$point \le 25 \text{ N/cm}^2$						
saicin + diclofen	ac gel % diclofenac sodium, 2 g formulat	ion (40 mg diclofense						
		ion (40 mg diciotenac						
sodium, 1.5 mg capsaicin) twice daily Topical								
Capsaicin gel								
0.075% Capsaicin, 2 g formulation (1.5 mg capsaicin) twice daily								
ical								
ofenac gel								
	m 2 g formulation (40 mg diclofe	nac) twice daily						
	ini, 2 g formulation (40 mg dictore	mac) twice dairy						
icai								
ebo gel								
	ormulation twice daily							
ical	J							
ening and start o	of treatment at the same visit (Visit	1)						
	od							
 Primary endpoint: Change in POM_{WP} (for the worst procedure, i.e. the procedure leadin to maximum pain) between baseline and Day 2 evening, 1 hour after drug application Key secondary endpoints POM_{WP}AUC₇₂ (Area under the curve of POM_{WP} assessed until Day morning, i.e. 72 hours after start of treatment) POM_{WP}AUC₁₂₀ (Area under the curve of POM_{WP} assessed until Day morning, i.e. 120 hours after start of treatment) Other secondary endpoints: Number of patients with a decrease in POM_{WP} of at least 30% from 								
	ebo gel applicable, 2 g frical rening and start or y treatment perior y follow-up perior ary endpoint: Change in P to maximum drug applicate secondary endpoint secondary endpoint polymorning, i.e. POMWPAUC	ebo gel applicable, 2 g formulation twice daily ical eening and start of treatment at the same visit (Visit y treatment period y follow-up period hary endpoint: Change in POM _{WP} (for the worst procedure, i.e to maximum pain) between baseline and Day 2 drug application secondary endpoints POM _{WP} AUC ₇₂ (Area under the curve of POM morning, i.e. 72 hours after start of treatment) POM _{WP} AUC ₁₂₀ (Area under the curve of POM						

c03317678-02 Trial Protocol Page 4 of 69

Proprietary confidential information © 2016 Boehringer Ingelheim International GmbH or one or more of its affiliated companies

Name of company:		Boehringer Ingelheim	
Name of finished product	:		
Name of active ingredien	t:	Diclofenac + Capsaicin	
Protocol date:	Trial number:		Revision date:
09-Dec-2015	1358.1		21-Jun-2016
Safety criteria:	 baseline on I Change in Po Change in Po evening, befo Change in Po 	patients with a decrease in POM _{WP} Day 2 evening, 1 hour after drug a OM _{WP} between baseline and the nessure Algometry (PA) between lore drug application A between baseline and the morning of adverse events, physical examples of adverse events, physical examples of adverse events.	pplication norning of Day 6 paseline and Day 2 ng of Day 6
	safety laboratory para	ameters, patient and investigator a	, ,

Vital signs	X																				X	
Physical examination	X																					
Pain On Movement (POM) ^L	X		X^{I}				X^{l}	X		XI			X ^l				X ^l				X	
Pressure Algometry (PA)	X				X			X			X				X						X	
Urine pregnancy test ^E	X																					
Safety laboratory tests	X																				X	
	X		X^{G}		X		X^N	X		X^N	X		X^N		X		X^N		X^{M}		X	
	X			X^{F}						X^{F}				X^{F}				X^{F}		X^{F}		
Review of in-/exclusion criteria	X																					
Randomization via Interactive Response Technology (IRT)	X																					
Weighing of trial medication/drug accountability	X																				X	
Dispense of trial drug and gloves; Instructions on use	X																					
Application of trial drug		X		X		X			X			X		X		X		X	X	X		
Dispense rescue medication; Instructions on use			X														X^{J}					

BI Trial No.: 1358.1

c03317678-02 Trial Protocol Page 6 of 69

Proprietary confidential information © 2016 Boehringer Ingelheim International GmbH or one or more of its affiliated companies

Visit ^K 1			Hm		2			3			4		Hm		5		Hm		m	6	7T Fllw up	
Day		1					2	2				3	3			4	4		5	D	6 ^D	8 ^D
Time window for visits		±0				±0			±0			±0				±0					-1/+2	-1/+4
Approximate day time ^B		M		E		$\mathbf{M}^{\mathbf{C}}$			$\mathbf{E}^{\mathbf{C}}$			M		E		M		E	M	E	M	
Timing rel. to application ^H	Pre	Apl	Post	Apl	Pre	Apl	Post	Pre	Apl	Post	Pre	Apl	Post	Apl	Pre	Apl	Post	Apl	Apl	Apl		
Hand-out of patient diary;			X				X			X			X				X					
Instructions on use																						
Assessment of skin reactions			X^N				X^N			X^N			X^N				X^N				X	
			X^{G}				X^{G}															
				X^{F}						X^{F}				X^{F}				X^{F}		X^{F}		
			X^{G}																			
Patient diary: Use of												Conti	nuousl	3 7								
rescue/other medication												Conti	nuousi	у								
Transfer of patient diary																						
entries to electronic Case						X			X			X				X					X	
Report Form (eCRF)																						
Return of patient diary						X			X			X				X					X	
Overall																						
tolerability assessment by																					X	
patient and by investigator																						
Return of trial drug and												X										
rescue medication																						
Adverse events			X			X			X			X				X					X	X
Completion of patient																					X^{A}	X^{A}
participation																					Λ	Λ

- A Completion of patient participation also needs to be completed if the patient withdraws prematurely following randomization (see Section 3.3.3)
- B M = Morning; E = Evening; Morning visits should generally be performed between 7:00 am and 11:00 am.
- C Visits 2 and 3 need to be planned so that the evening application of the trial medication can be administered 12 hours (±4 hours) after the morning application.
- Date of Visit 6 has to be agreed based on patient's availability and severity of pain. Standard treatment duration is 5 days (Day 1-5) with Visit 6 on Day 6. Treatment could be shortened to 4 days (with Visit 6 on Day 5) or extended to 6 days (with Visit 6 on Day 7; home procedures indicated in the Flow Chart for Day 5 to be repeated on Day 6) or 7 days (with Visit 6 on Day 8; home procedures indicated in the Flow Chart for Day 5 to be repeated on Day 6 and 7). Visit 7T should be performed at least 2 days and no later than 4 days after Visit 6.
- E For women of childbearing potential only

c03317678-02 Trial Protocol Page 7 of 69

Proprietary confidential information © 2016 Boehringer Ingelheim International GmbH or one or more of its affiliated companies

- G Parameters to be assessed by the patient 0.5 (±5 min), 1 (±10 min but before POM assessments), 3 (±15 min) and 6 (±15 min) hours after the morning application of the trial drug. Results will be entered into the patient diary.
- H Pre = before application; Apl = Application; Post = after application. The application time at each visit is to be documented in the eCRF.
- I Assessment 1 hour (± 10 min) after application of trial medication
- J Optional second dispense of rescue medication
- K Hm = Home procedure; Fllw up = Follow up
- L All five POM assessments need to be performed at Visit 1 before application. Once POM_{WP} is determined, only POM_{WP} and the other POM procedures related to the same stratum (either back or neck pain) as POM_{WP} need to be performed at subsequent assessments (see Section 5.2.1)
- M To be assessed by the patient at home directly before and 1 hour (±10 min) after the morning application of the trial drug
- N To be assessed 1 hour (±10 min) after application of the trial drug and before POM assessments

BI Trial No.: 1358.1

c03317678-02 Trial Protocol Page 8 of 69

Proprietary confidential information © 2016 Boehringer Ingelheim International GmbH or one or more of its affiliated companies

TABLE OF CONTENTS

TITLE I	PAGE	1
CLINIC	AL TRIAL PROTOCOL SYNOPSIS	2
FLOW (CHART	5
TABLE	OF CONTENTS	8
ABBRE	VIATIONS	11
1.	INTRODUCTION	13
1.1	MEDICAL BACKGROUND	13
1.2	DRUG PROFILE	14

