1. INTRODUCTION

1.1 MEDICAL BACKGROUND

Back pain is a very common disorder with a point prevalence of approximately 35% in Germany [P11-08387]. In most cases specific causes cannot be identified (i.e. "unspecific low back pain"). Usually, low back pain is a self-limiting disorder, and approximately 90% of patients experience remission within 6 weeks. Musculoskeletal pain in the back area is worsened through a vicious circle of excessive muscle (force) load inducing pain (by minor muscle injury and local muscle ischaemia) that causes non-physiological posture, which in turn causes further pain.

Neck pain is becoming increasingly common throughout the world. The point prevalence of neck pain ranges from 0.4% to 41.5% (mean: 14.4%); and 1 year prevalence ranges from 4.8% to 79.5% (mean: 25.8%). Prevalence is generally higher in women, higher in highincome countries compared with low- and middle-income countries and higher in urban areas compared with rural areas [R12-4817]. Much neck pain is not attributable to a specific disease or disorder and is labelled as "soft-tissue" rheumatism or muscular/ mechanical/ postural neck pain [R15-2389].

Acute back/ neck pain is often treated with over the counter (OTC) analgesics, such as paracetamol, ibuprofen, or naproxen. Other treatment options are local heat [P11-08754] and hyperaemisation inducing agents [R11-2672]. Local heat and hyperaemisation inducing treatment were shown to augment blood flow and haemoglobin oxygenation in the skin and in the muscles [R11-2636, P11-05079]. Thus, such treatments can be assumed to be beneficial in the treatment of such musculoskeletal conditions.

Remedies against acute back/ neck pain, especially in an OTC environment, are required to reduce back discomfort fast and effectively while being tolerated well.

NSAIDs have been used since decades for the treatment of back and neck pain. A systematic review concluded that NSAIDs are effective for short-term symptomatic relief in patients with acute and chronic low back pain without sciatica. However, effect sizes are small [P08-09510]. In a recent review [P15-04711] topical options for the treatment of back/neck pain has been discussed. In a clinical trial a hyperaemisation inducing agent has been shown to reduce back/neck pain with low incidence of side effects [P11-00252].

Topically applied remedies seem to have a low potential for systemic side effects and interactions with other (including systemic) medications.

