3. DESCRIPTION OF DESIGN AND TRIAL POPULATION

3.1 OVERALL TRIAL DESIGN AND PLAN

This trial is a prospective, randomised, double-blind, parallel group, multi-centre trial to show superiority in terms of reduction of Pain on Movement (POM) of a topical combination containing diclofenac 2% and capsaicin 0.075% compared to placebo, as well as to diclofenac 2% and capsaicin 0.075% when applied twice daily over 4 to 7 days to patients with acute back pain or neck pain. A total of approximately 800 patients will be randomised to the treatment groups diclofenac + capsaicin, diclofenac, capsaicin and placebo in a 3:3:3:1 ratio in order to achieve 700 patients eligible for the assessment of the primary endpoint.

After a screening evaluation (Visit 1), eligible patients will be randomised into the double-blind treatment phase of the trial. After administration of the first treatment, the patients will administer the second application of the trial medication in the evening at home. They will return to the trial site for four more visits (Visits 2 to 5) in the morning and in the evening of the following day (Day 2) and in the morning of Days 3 and 4 and thereby be dosed while at the site. Evening applications on Day 3 and Day 4 will be administered by the patients at home. Thereafter, the treatment will be administered at home for one more day (Day 5). The patients will then return to the trial site for final assessments (Visit 6) in the morning of Day 6. The trial participation will be concluded by a telephone call (Visit 7T) for follow-up on adverse events (AEs) on Day 8.

Depending on the severity of a patient's condition and on a patient's availability, the treatment-period at home (Day 5) could be skipped or extended by one or two days. Visit 6 should then be performed on the day immediately following to that shortened or extended period.

The interval between two applications of the trial medication should be 12 hours. This interval could be shortened or extended by 4 hours as long as no more and no less than two applications are administered on each treatment day.

Patients who discontinue the application of the trial medication prematurely, should be encouraged to contact the site immediately so that Visits 6 and 7T could be performed on the day immediately after discontinuation.

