3.2 DISCUSSION OF TRIAL DESIGN, INCLUDING THE CHOICE OF CONTROL GROUP(S)

The study design of this trial is based on the Guideline on Clinical Development of Fixed Combination Medicinal Products of the EMA's Committee for Medicinal Products for Human Use (CHMP) [R09-2704]. The design is suited to assess the effect of a gel containing diclofenac and capsaicin on acute back or neck pain compared with gels containing the individual components, diclofenac or capsaicin, or placebo. Comparison with the individual components is necessary to confirm a clinically meaningful effect of the combination in terms of pain relief. Comparison with placebo is necessary to assess the overall relative effect of the combination of diclofenac and capsaicin.

Assessment of pain at rest provides important information on patients comfort during treatment [P08-09626]. However, for measurement of pain at rest patients tend to move into a relieving posture which limits the value of the measurement to reflect patient's restriction in performing daily activities. Other than at rest, functional limitations become obvious during movement. Functional improvement can be detected by standardized movements [R14-1467]. Thus, POM was selected as the primary variable for assessment of pain relief. For back and neck pain standardized movements have been established [R14-1467, R12-4427].

For the assessment of the primary endpoint, POM_{WP} 1 hour after the evening application on Day 2 will be compared to POM_{WP} at baseline. Typically a treatment effect of topical treatments can be observed after 1 to 3 days. The chosen time frame for assessment of the primary endpoint allows sufficient time for the trial treatment to become effective. On the other hand it is sufficiently short to avoid diminishing differences by the self-limiting properties of acute back or neck pain. Similar time frames were chosen in comparable clinical trials [R14-1467, R12-4427].

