6.2.3 Follow Up Period and Trial Completion

All study procedures according to the Flow Chart should be performed.

Patients who want to discontinue the trial treatment prematurely should be asked to have Visit 6 in the morning after the last application of the trial medication and to have a Visit 7T at least 48 hours after that last application.

Patients who at the end of their trial participation still require treatment for the trial indication should be treated according to local standard of care.

Proprietary confidential information © 2016 Boehringer Ingelheim International GmbH or one or more of its affiliated companies

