7.3.1 Primary endpoint analyses

The primary endpoint 'Change in POM_{WP} between baseline (before application at Visit 1) and Visit 3 (Day 2 evening, 1 hour after application)' will be analysed utilising a restricted maximum likelihood (REML) based repeated measures approach, using all available longitudinal POM_{WP} observations at the assessment times T1 = Visit 1 (Day 1 morning, 1 hour after application), T3 = Visit 2 (Day 2, morning, 1 hour after application, T4 = Visit 3 (Day 2 evening, before application) and T5 = Visit 3 (Day 2 evening, 1 hour after application). The statistical model will be applied to the analysis of change from baseline (T0 = Visit 1 morning, before application) in POM_{WP} at times T1, T3, T4 and T5. The statistical model will include the fixed, categorical effects of treatment, country, application site (back/neck), time and treatment-by-time interaction, as well as the continuous, fixed covariates of baseline POM_{WP} and baseline-by-time interaction. The definition of baseline POM_{WP} is given in Section 7.1.

An unstructured covariance structure will be used to model the within-patient errors. In case this analysis fails to converge, other covariance structures to be employed will include Compound Symmetry, Autoregressive Model, AR (1) and Spatial Covariance, with the covariance structure converging to the best fit, as determined by Akaike's information criterion, to be used for purposes of comparing treatment effects. The Kenward-Roger approximation will be used to estimate the denominator degrees of freedom [R11-1488].

Differences between the treatment group effects (diclofenac/capsaicin - diclofenac, diclofenac/capsaicin - capsaicin, diclofenac/capsaicin - placebo) with regard to the change in POM_{WP} between T0 and T5, calculated as ' POM_{WP} at time T0 - POM_{WP} at time T5' (see Section 5.1) will be estimated by reference to the adjusted least square means and the corresponding 95% confidence intervals (CI). All statistical testing will be performed using a two-sided, alpha = 0.05 level of significance.

The primary analysis will be based on the full analysis set (FAS) as defined in Section 7.3.

In addition to the primary analysis, a separate analysis will be performed to test the heterogeneity of the strata 'application site' and 'country', respectively. In these models the two interaction terms treatment-by-stratum-by- time and stratum-by-time will be added to the primary model, respectively.

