7.3.2 Secondary endpoint analyses

The key secondary and other secondary endpoints will be analysed with the treated set as defined for efficacy analysis in Section 7.3.

The key secondary endpoints of $POM_{WP}AUC_{72}$ and $POM_{WP}AUC_{120}$ will be analysed using an analysis of covariance (ANCOVA) including treatment, country and application site (back/neck) as fixed effects and the baseline POM_{WP} as a continuous covariate. Treatment differences will be estimated by reference to the adjusted least square means and the corresponding 95% confidence intervals. The statistical testing will be performed using a two-sided, alpha = 0.05 level of significance.

The number of patients with a decrease in POM_{WP} of at least 30% from baseline until Day 2 evening, 1 hour after drug application, will be analysed by a logistic regression model, adjusting for the categorical covariates country and application site (back/neck). The likelihood-ratio test will be used to test for differences between treatments. Adjusted odds ratios together with 95% confidence intervals will be used to quantify the effect of treatment, comparing all treatments to the treatment of diclofenac/capsaicin as the reference treatment.

The number of patients with a decrease in POM_{WP} of at least 50% from baseline until Day 2 evening, 1h after drug application, will be analysed correspondingly.

The change in POM_{WP} between baseline and the morning of Day 6 will be analysed analogously to the primary endpoint. The statistical model will be applied to the analysis of change from baseline (T0 = Visit 1 morning, before application) in POM_{WP} at times T1, T3, T4, T5 and - additionally at times T7 (=Visit 4 = Day 3 morning, 1 hour after application), T9 (= Visit 5 = Day 4 morning, 1 hour after application) and T12 (= Visit 6 = morning of Day 6).

The change in PA between baseline and Day 2 evening, before drug application (Visit 3) will be analysed analogously to the primary endpoint using all available longitudinal PA observations at the assessment times T2 = Visit 2 (Day 2 morning, before application) and T4 = Visit 3 (Day 2, evening, before application). The statistical model will be applied to the analysis of change from baseline (T0 = Visit 1 morning, before application) in PA at times T2 and T4.

The change in PA between baseline and the morning of Day 6 will be analysed analogously to the primary endpoint. The statistical model will be applied to the analysis of change from

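### The two supportive Day 6 models (POM_WP and PA) enter Visit 6 as one fixed time, although pain severity may help set its day and early stoppers may have it on Day 2 to 4

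*Protocol*

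**What the plan says.** **When Visit 6 happens.** Flow Chart footnote D: "Date of Visit 6 has to be agreed based on patient's availability and severity of pain". The standard is Day 6, with Day 5, 7 or 8 allowed. Protocol 3.1 gives the same two grounds: "Depending on the severity of a patient's condition and on a patient's availability". Under Protocol 6.2.3, patients who want to stop treatment early "should be asked to have Visit 6 in the morning after the last application of the trial medication". A patient whose last dose is on Day 1, 2 or 3 would therefore have Visit 6 on Day 2, 3 or 4.

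**How it is analysed.** Protocol 7.3.2 analyses the change to the morning of Day 6 in POM_WP and in PA analogously to the primary model. For that model, Protocol 7.3.1 states: "The statistical model will include the fixed, categorical effects of treatment, country, application site (back/neck), time and treatment-by-time interaction", plus baseline and baseline-by-time. Actual day is not among the terms. Both Day 6 models define the last time point as "T12 (= Visit 6 = morning of Day 6". SAP 7.5.2.1 and 7.5.2.2 refer back to the protocol without adding a timing rule.

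**How off-schedule visits are placed.** SAP 6.7 gives Visit 6 a window of -1/+2 days, flags visits outside their window as protocol violations, and assigns a single out-of-window visit to its scheduled visit. If two consecutive visits are missed and one visit takes place between them, that visit goes to the closest scheduled one, with final assignment agreed at a review meeting.

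**Status.** Protocol 7.2 makes both Day 6 endpoints supportive only.

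**The concern.** T12 is labelled as one moment but pools scores from about 96 to 168 hours after the start of treatment, and earlier ones from early stoppers. Moves made only for availability do no harm. Moves made for pain severity are different, because severity after randomisation is an outcome. If the combination works better, its patients may be seen on different days from those in the comparator arms.

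The day matters because the condition improves by itself. Protocol 3.2 chose an early primary time point because of the "self-limiting properties of acute back or neck pain". If patients with less pain are seen earlier and those with more pain later, the arm doing worse gets extra recovery time and the T12 contrast shrinks. Early stoppers are a separate matter: a Day 2 to 4 score labelled as Day 6 can favour either arm, depending on who stops and why.

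At stake is the reading of two supportive contrasts. The plan's confirmatory primary result does not depend on them.

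**Working it through.** The plan gives no figure for Visit 6 timing. Its only power statement (Protocol 7.7: 98% and 82% for a 12 mm difference and SD 30 mm) concerns the primary endpoint and reproduces: a two-sample t-test gives 98.3% with 210 against 210 patients and 82.3% with 210 against 70. Only the 12 mm and 30 mm are borrowed below.

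**Formula.** Shift in the T12 contrast ≈ (arm difference in mean Visit 6 day) × (daily change in pain).

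**Inputs**
- Gap between arms: 12 mm / 30 mm = 0.4 SD (Protocol 7.7, a Day 2 assumption carried to Day 6).
- Share moved: 10%, 25% or 33% in each direction, 1 day earlier or 1.5 days later on average (assumed).
- Direction: more pain means a later visit (assumed; no text says so).
- Slope: Protocol 1.1 says of low back pain that "approximately 90% of patients experience remission within 6 weeks". A crude straight line from 50 to 100 mm down to zero over 42 days gives 50/42 = 1.2 to 100/42 = 2.4 mm/day. Slopes of 3 to 8 mm/day are a pure assumption.

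**Step 1: difference in days.** Put the arms at ±0.2 SD with common cut-offs. For 25% each way the cut-off is 0.69 SD; the arms exceed it with probability 31.3% and 18.7%, a difference of 12.5 points. By symmetry the same difference applies at the lower cut-off.

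| Moved each way | Arm difference per cut-off | Days = difference × (1 + 1.5) | If half pain-driven |
|---|---|---|---|
| 10% | 6.8 points | 0.17 | 0.09 |
| 25% | 12.5 points | 0.31 | 0.16 |
| 33% | 14.4 points | 0.36 | 0.18 |

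**Step 2: shift in POM_WP, smallest to largest**
- At 1.2 to 2.4 mm/day: from 0.085 × 1.2 = 0.10 mm (10%, half pain-driven) to 0.36 × 2.4 = 0.86 mm (33%, fully pain-driven).
- At 3 to 8 mm/day: from 0.085 × 3 = 0.26 mm to 0.359 × 8 = 2.87 mm.
- With a 6 mm gap at Day 6 instead of 12 mm: 0.05 to 0.43 mm at the lower slopes, and at most 1.45 mm at the higher ones.
- Moves for availability only: zero.

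**Step 3: early stops.** Assume that the share seen before Day 5 differs between arms by 1 to 5 points and that these patients are seen 2 to 3 days early. The shift is then 0.01 × 2 × 1.2 = 0.02 mm to 0.05 × 3 × 2.4 = 0.36 mm, or up to 0.05 × 3 × 8 = 1.2 mm at the steepest assumed slope, in either direction.

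**PA.** The difference in days carries over, but the documents give no daily change in PA, so no size is claimed.

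**Where early-stop scores belong.** The morning POM_WP times in the model are 1 hour post-dose, for example "T9 (= Visit 5 = Day 4 morning, 1 hour after application". An early-stop Visit 6 has no dose that morning, so it matches none of them. PA is measured before application, so an early-stop PA score does match a slot: T2 on Day 2 and, from the numbering and the flow chart, T6 on Day 3 or T8 on Day 4.

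**The case against.** The case for leaving the plan alone is fair. The window is declared openly in the flow chart, Protocol 3.1 and SAP 6.7. Dosing continues to the evening before Visit 6 (Protocol 4.1.4), so the visit can be read as an end-of-treatment measurement, and entering a windowed visit at its nominal time is ordinary practice. The direction is assumed, availability is the other stated ground, and a diluted supportive contrast does not produce a false claim of superiority. SAP 7.7 already summarises days on treatment by arm, which nearly gives the actual Visit 6 day. All of this stands and keeps the point minor. It does not explain why a Day 2 to 4 score should count as the morning of Day 6.

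A reader might infer that the Day 6 result could lose 2 to 3 mm. The documents do not support that: it needs slopes that they do not give, a Day 2 gap persisting to Day 6, and half to two thirds of patients off the standard day. A reader might also infer that every early-stop score is certain to enter T12. The closest-visit rule and the review meeting could place some elsewhere, and the SAS code cited in SAP 7.4.1 is not in the public text, so a further timing rule cannot be excluded.

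A sensitivity model counting only Day 6 scores as T12 looks attractive but is a poor trade. In a simulation with a true difference of 12 mm and 25% moved each way, it recovers 12.0 mm if the Day 4 score sets the date. If pain at home that the model does not contain sets the date, it returns about 5.6 mm, against 9.5 to 11.0 mm for the planned analysis (slopes 3 to 8 mm/day). Its standard error is also larger, at about 3.7 mm against 2.6 to 2.8 mm.

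**Conclusion.** The point holds as a minor one. In the published text, T12 mixes measurement days that can depend on pain after randomisation, and the single-visit rule would place early-stop scores from Day 2 to 4 there. The primary endpoint and AUC72 are unaffected.

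For Day 5 to 8 moves the bias is probably small and conservative: about 0.1 to 0.9 mm in POM_WP, assuming that more pain means a later visit, a 12 mm gap at Day 6 and a straight-line recovery over six weeks. Larger figures need assumed slopes of 3 to 8 mm/day. Early stops can act in either direction, and the size for PA is unknown. Confidence is medium, because the slope, the share moved and the direction are all assumptions.

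**What to change.** Two additions to SAP 6.7 and 7.5.2:

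- **(a) Early stops.** Do not enter Visit 6 scores taken before Day 5 as T12. Enter early-stop PA scores at the matching pre-application morning time (T2, T6 or T8) if that slot is empty. List early-stop POM_WP scores separately.
- **(b) Day 5 to 8.** Keep these scores in the main analysis and report the actual Visit 6 day by arm. Beside each contrast, give the arm difference in mean Visit 6 day times the pooled daily change from Day 3 to Day 4 (T7 to T9 for POM_WP, T6 to T8 for PA), as an approximate upper size of the timing shift.

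Do not add a Day-6-only sensitivity model.

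**Cost.** Some SAP wording and one product of two summary figures per endpoint, from dates and scores already recorded; days on treatment in SAP 7.7 plus one largely gives the Visit 6 day. With (a), T12 is missing for the early stoppers concerned, presumably few, and is handled under the existing no-imputation rule. The figure in (b) overstates the shift if recovery slows: in the simulation at 3 to 8 mm/day, by about 0.4 to 1.2 mm when the daily change halves after Day 4.
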